### **9.2 Efficacy Assessments**

All in clinic assessments will be performed pre-dose.

#### **9.2.1 Itching, Scratching, and Sleep Score**

Itching, observed scratching, and sleep disturbance will be recorded twice each day via eDiary. Patients and/or caregivers will be instructed to complete the eDiary every day in the morning after the patient wakes and in the evening just before the patient goes to sleep throughout the study. Patients and caregivers will receive a formal training session during Screening Visit 1. During Screening Visit 2, parents and caregivers will be retrained if necessary. When logistically feasible, the same parent or caregiver should record in the eDiary, and changes to the parent or caregiver who is performing the recording should be minimized. If a new parent or caregiver will begin to complete the Albireo ObsRO eDiary during the course of the trial, they will be provided with training during a clinic visit before they begin to use the eDiary. The caregiver recording in the eDiary will be recorded.

The eDiary includes Albireo ObsRO and PRO items. Patients  $< 8$  years of age at time of signing the ICF will not be asked to complete the Albireo PRO items; only the Albireo ObsRO eDiary will be completed by caregivers of patients in this age group. Older patients, 8 to 18 years of age at time of signing the ICF, will complete the Albireo PRO items and the caregiver will complete the Albireo ObsRO items. Patients  $\geq 18$  years of age at signing of the ICF will complete the PRO; no caregiver information will be collected. The Albireo PRO items assess severity of itch, aspects of sleep disturbance (morning diary only), and tiredness. For patients 8 to 12 years of age, the caregiver will read the Albireo PRO items along with the child and record the child's response. A guide will be provided to the caregivers that provides standardized explanations of the Albireo PRO items, in case the patient is confused or requires clarification about the meaning of a question. The Albireo ObsRO items assess severity of observed scratching, aspects of observed sleep disturbance (morning diary only), and signs of tiredness (evening diary only). The Albireo ObsRO and PRO scratching and itch severity items use 0 to 4 response scales, where each response is distinguished by a unique facial expression, verbal anchor, number, and color code ([Appendix 2](#)). To meet eligibility criteria, a scratch score will be calculated from daily diary entries (ObsRO items) the 14 consecutive days prior to randomization.

A daily AM and PM score for the Albireo ObsRO scratching item will be averaged from the 2 ratings for each day. The AM score captures nighttime symptoms and the PM score captures daytime symptoms.

### **9.2.2 Serum Bile Acids**

Blood samples for analysis of fasting total serum bile acid will be drawn at all clinic visits. Patients will fast (water intake only is permissible) for at least 4 hours prior to the collection of samples for serum bile acid. Exceptions can be made for infants, <12 months of age, if unable to fast for the full 4 hours. Any visit at which a bile acid sample result is unreportable, an additional unscheduled visit for a repeat sample collection may be scheduled. All post baseline serum bile acid will be blinded. Samples will be processed and transported to a central laboratory per instructions in the laboratory manual.

### **9.2.3 Quality of Life Questionnaire (PedsQL)**

Patients and caregivers will be asked to complete a QoL questionnaire (PedsQL) at randomization (Study Day 1), Week 12, Week 24/EOT visits. Details of the questions included on the questionnaire are provided in [Appendix 4](#).

### **9.2.4 Biochemical Markers and PK Samples**

Blood samples for analysis of clinical chemistry will be drawn during Screening Visits 1 and 2, as well as at randomization (Study Day 1), Week 4 to 24/EOT, and Safety Follow-up visits. As outlined in [Table 4](#), total bilirubin, AST, ALT, and gamma glutamyl transferase assessments are included as part of the routine laboratory parameters. Blood samples for autotaxin and p-C4 will be drawn at randomization (Study Day 1), Week 12, and Week 24/EOT, only for children with body weight >10 kg. Blood for Odevixibat PK assessment will be drawn at Week 4, Week 20, and EOT (only for children with body weight >10 kg). When a patient meets criteria for close observation due to suspected DILI ([Section 10.2.2.2](#)) samples will be collected for FGF19, p-C4, and PK within 3 days if possible (only for children with body weight >10 kg). Samples will be processed and transported to a laboratory per instructions in the laboratory manual.

### **9.2.5 Global Impression of Change and Global Impression of Symptom Measures**

Patients ( $\geq 8$  years of age), caregivers, and clinicians will complete GIC (PGIC, CaGIC, and CGIC) and the GIS measures (PGIS, CaGIS, CGIS) ([Appendix 3](#)) at randomization (Study Day 1; PGIS only), Week 4, 12, and 24/EOT.

The GIC items assess change in itch (patient version), scratching (caregiver and clinician versions), and sleep (all versions) since starting the study drug. The GIS items assess itch (patient version), scratching (caregiver and clinician versions), and sleep (all versions) in the past week. Caregivers and clinicians will complete the GIC and GIS for all patients; those patients  $\geq 8$  years of age will complete the patient version.

### **9.2.6 Clinician Assessment of Xanthoma**

Changes in xanthoma as assessed by the Clinician Xanthoma Scale will be measured at randomization (Study Day 1), Week 12, and Week 24/EOT visits. The clinician's assessment of the participant's xanthomatosis is focused on the number of lesions present and the degree to which the participant's lesions interfere or limit his or her activities. The clinician xanthoma scale uses a 5-point scale, in which 0 represents no evidence of xanthomatosis, 1 represents fewer than 20 scattered individual lesions, 2 represents more than 20 lesions that do not interfere with or limit activities, 3 represents large numbers of lesions that by their large numbers or size cause distortion of the face or extremities, and 4 represents xanthomas that interfere with function (such as hand use or ability to walk) because of excess size or number.

## 10 ASSESSMENT OF SAFETY

The timing and frequency of safety assessments are described in [Section 7.1.3](#) and in [Table 1](#) above. For each study visit all assessments will be performed pre-dose.

The primary safety analysis for this study will include the incidence of total treatment-emergent AEs (TEAEs) and TEAEs categorized by causality, severity, and seriousness assessments made by the investigator by comparing study drug exposure to placebo.

Trends in safety will also be evaluated for the following assessments:

- Physical examinations
- Concomitant medications
- Vital signs
- Laboratory test results (including clinical chemistry, hematology, urinalysis, AFP, vitamins A and E, 25-hydroxy vitamin D and INR)
- Liver ultrasound and elastography (where available)
- Discontinuations due to AEs

### 10.1 Adverse Events

#### 10.1.1 Safety Reporting Period

Each patient must be carefully monitored for the development of AEs during the safety reporting period.

The safety reporting period for adverse events is from the first dose of study drug through the last planned study visit or 28 calendar days after the last dose of the study drug, whichever occurs later. The safety reporting period for serious adverse events is from signing of the informed consent form through the last planned study visit or 28 calendar days after the last dose of the study drug, whichever occurs later.

An SAE that occurs following the safety reporting period and which is assessed by the investigator as related to study medication should also be reported.

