## 2 STUDY SYNOPSIS

Name of Sponsor/Company: Albireo AB	Name of Product: Odevixibat	Name of Active Ingredient: Odevixibat
Title of Study: A Phase 3 Double-blind, Randomized, Placebo-controlled Study of the Safety and Efficacy of Odevixibat (A4250) in Patients with Alagille Syndrome (ASSERT)		
Study Centers: Approximately 35 sites will be initiated for this study North America, Europe, Middle East, and Asia Pacific.		
Publication(s): None.		
Planned Study Period: 2020 to 2021	Development Phase: Phase 3	
Primary Objective: To demonstrate the efficacy of repeated daily doses of 120 µg/kg/day odevixibat in relieving pruritus in patients with ALGS.		
Secondary Objectives: To assess the impact of odevixibat on serum bile acid levels in patients with ALGS. To evaluate the safety and tolerability of odevixibat in patients with ALGS.		
Methodology: This study includes a screening period of up to 56 days, followed by a 24-week treatment period, and a safety Follow-up Period. Screening Period: Two Screening visits will occur to establish eligibility and provide electronic diary (eDiary) instructions for recording the observer-reported outcomes (ObsRO) and patient reported outcomes (PRO) for pruritus. Treatment period: On Day 1, patients will be randomized 2:1 to receive odevixibat 120 µg/kg/day or placebo. The treatment period duration is 24 weeks. Safety Follow-up Period: A Safety Follow-up visit will take place 28 days (±7) following the Week 24/EOT visit or the date of last dose for patients who prematurely discontinue study drug. Patients who complete the Week 24/EOT visit in this study will be invited to participate in an open-label extension study in which all patients will receive active treatment. Patients who enroll in the open-label extension study will not participate in the Safety Follow-up Period.		
Number of Patients: Approximately 45 patients <18 years of age at randomization with a genetically confirmed diagnosis of ALGS will be enrolled. An additional exploratory cohort of patients ≥18 years of age with genetically confirmed diagnosis will be enrolled not to exceed 18 patients in total.		

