- i Includes training on use of the device at Screening Visit 1, retraining (if applicable) at Screening Visit 2, and review of patient daily entries during 14 days prior to Day 1 to determine eligibility. eDiary compliance will be reviewed at all visits and the Day 14 phone call.
- j See [Table 4](#) for detailed parameters.
- k Patients will fast (water intake only is permissible) for at least 4 hours prior to the collection of samples for serum bile acid and vitamin A. Exceptions can be made for infants, less than 12 months of age, if unable to fast for the full 4 hours.
- l Samples will not be collected for patients  $\leq 10$  kg. In the event of an SAE, samples are to be collected as close to the onset of the event as possible.
- m For females who have reached menarche. If a urine pregnancy test is positive, a serum pregnancy test is to be performed to confirm the pregnancy.
- n Study drug to be taken once daily from randomization (Study Day 1) through the Week 24/EOT visit as described in [Section 7.1](#) and [7.1.2.2](#).
- o Serious adverse events will be collected from the time of signing of the ICF through study completion. Non-serious adverse events will be collected from the first dose of study drug through study completion. See section 10.1.1 for additional information.

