### 7.1.3 Safety Follow-Up

The Safety Follow-up visit is required 28 days ( $\pm 7$ ) following the Week24/EOT visit. For patients prematurely discontinued study treatment, this visit is not required if the EOT visit occurs more than 3 weeks after the last dose of study drug ([Section 7.1.4](#)). This visit is not required for patients who enroll in the open-label extension study within 28 days of the Week 24 Visit.

The following procedures and assessments will be performed:

- Review of concomitant medications
- Skin examination ([Section 10.2.5](#))

- Vital signs ([Section 10.2.7](#))
- Clinical chemistry, hematology, and urinalysis ([Section 10.2.1](#))
- Serum bile acid ([Section 9.2.2](#))
- INR
- Urine pregnancy test for females who have reached menarche
- AE monitoring and FSV deficiency questionnaire

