### **7.2.5 Termination of Study Participation**

Participation in the study will be completed for each individual patient when one of the following occurs:

- Week 24 visit: for patients who complete the treatment period and enter an open-label study within 28 days of the Week 24 visit
- Safety Follow-up visit: for patients who complete the treatment period and do not enter an open-label study within 28 days of the Week 24 visit
- For patients who withdraw consent or assent, the date of withdrawal of consent or assent
- For patients who are lost to follow-up ([Section 7.2.3](#)), the date of study participation completion will be defined as the date of the last contact

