#### **10.1.3 Recording of Adverse Events**

Patients must be carefully monitored for the development of any AEs during the safety reporting period.

All observed AEs and any AEs that are spontaneously reported by the patient/caregiver will be recorded by the investigator. For all AEs, the severity, seriousness, and causality to study drug for each AE as outlined in [Section 10.1.2](#) will be assessed and recorded in the eCRF.

Any AE assessed as serious must be reported within 24 hours of site awareness.

Any SAEs or AEs that lead to permanent discontinuation of study drug that are unresolved at the time of the last study visit will be followed up by the investigator until resolution or stabilization. Following the last study visit, the Sponsor will provide forms for reporting additional information for any patient with ongoing SAEs or AEs that led to permanent discontinuation of study drug. Albireo retains the right to request additional information for any patient with ongoing AE(s) or SAE(s) at the end of the study.

Treatment-emergent AEs are defined as any AE that occurs after first dose of study drug. All SAEs that occur in the Screening Period, i.e. after enrollment and prior to first dose of study drug, will be collected as non-treatment emergent SAEs.

If there is a clinically significant deterioration of a laboratory value/vital sign or other routine study assessment that is associated with a diagnosis, the clinical diagnosis will be reported

as an AE and the associated signs and symptoms will be considered additional information unless the sign or symptom is more severe than expected given the diagnosis. For example, in a patient diagnosed with hepatitis during the safety reporting period, hepatitis would be considered the AE. Signs and symptoms of abdominal pain, vomiting, and elevated ALT and AST would not be reported separately unless, in the opinion of the investigator, one of these signs or symptoms is more severe than expected and therefore a separate AE assessment is indicated.

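### For patients who enter the open-label extension, AE/SAE collection has two end dates up to 28 days apart, and the SAP's event count and time at risk need not end on the same day

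*Protocol*

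**What the plan says.** **Collection, protocol.**

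- Section 10.1.1 starts the AE period at first dose and the SAE period at consent. Both run "through the last planned study visit or 28 calendar days after the last dose of the study drug, whichever occurs later". Entry into the extension is not mentioned. After the period, only SAEs judged related remain reportable.
- Table 1 footnote o: "Non-serious adverse events will be collected from the first dose of study drug through study completion". SAEs have the same end. The footnote then refers the reader to 10.1.1.
- Section 7.2.5 lists when participation is completed. One entry is "Week 24 visit: for patients who complete the treatment period and enter an open-label study within 28 days of the Week 24 visit".
- Section 7.1.3, on the Safety Follow-up visit: "This visit is not required for patients who enroll in the open-label extension study within 28 days of the Week 24 Visit". The synopsis is broader: "Patients who enroll in the open-label extension study will not participate in the Safety Follow-up Period".
- The synopsis describes the extension as "an open-label extension study in which all patients will receive active treatment", so former placebo patients start odevixibat there.

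**Counting, protocol and SAP.**

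- Protocol Section 10.1.3: "Treatment-emergent AEs are defined as any AE that occurs after first dose of study drug". No end is given.
- SAP Section 4.8.1 and Table 9 restrict TEAEs to events in the Treatment Period. The synopsis and SAP Section 1.1 give that period as 24 weeks, but the AE section names no end day.
- SAP Section 4.8.1 ends time at risk for a patient without the event at the last participation date, which Table 9 defines as last contact or death, whichever is first. Kaplan-Meier curves are censored at last contact.

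**The concern.** A site that follows footnote o and Section 7.2.5 stops collecting at Week 24. A site that follows Section 10.1.1 goes on for another 28 days. The same patient would yield different AE and SAE records depending on which page was used.

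Neither reading fits a rollover patient well. If collection stops at Week 24 and open-label drug starts later, the days between are off drug and outside this study's collection, apart from related SAEs. If collection runs to 28 days after the last dose and open-label drug starts at once, those 28 days are on odevixibat whatever the randomised arm. No passage ends collection at the first open-label dose.

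At stake are the completeness of safety data just after the last randomised dose, and whether the exposure-adjusted incidence rates have a numerator and a denominator that cover the same days.

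**Working it through.** **Inputs**

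- Treatment period: 24 weeks (synopsis; SAP Section 1.1).
- Drug taken up to the Week 24/EOT visit (Table 1 footnote n).
- Reporting tail: 28 days after the last dose (Section 10.1.1).
- Planned completers: about 36 of 45, randomised 2:1 (Section 11.1). Applying 2:1 to completers gives 36 × 1/3 = 12 placebo and 24 odevixibat.
- Gap g between Week 24 and the first open-label dose: not given. I assume 0 to 28 days, because Sections 7.1.3 and 7.2.5 treat rollover as entry within 28 days, and I take entry and first open-label dose to be the same day.

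**1. The two end dates**

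Week 24 is 24 × 7 = Day 168, the day in Table 1. Adding 28 days gives 168 + 28 = Day 196, which reproduces Table 1's target day for the Safety Follow-up visit (196 ± 7).

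- Footnote o with Section 7.2.5: collection ends at Day 168.
- Section 10.1.1: the last planned visit for a rollover patient is Week 24 and the last dose is at about the same time, so the later of the two limits is about Day 196.

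The difference is up to 28 days per rollover patient, or 28/168 = 16.7% of the treatment period.

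**2. What the disputed 28 days contain**

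They split into g days off drug and 28 − g days on open-label odevixibat.

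| Gap g (days) | Off drug, lost if collection stops at Week 24 | On open-label drug, included under 10.1.1 |
|---|---|---|
| 0 | 0 | 28 |
| 14 | 14 | 14 |
| 28 | 28 | 0 |

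The two consequences trade off. A patient cannot have 28 days of each.

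**3. Upper bound for placebo, if all 12 completers roll over**

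- Disputed time: 12 × 28 = 336 days; 336/365.25 = 0.92 patient-years.
- Their own 24-week exposure: 12 × 168 = 2,016 days; 2,016/365.25 = 5.52 patient-years.

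Both figures use the same 12 patients. The 0.92 is the total of off-drug and open-label time.

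**4. Event count against time at risk**

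The exposure-adjusted rate is the number of patients with the event divided by total time at risk. Suppose the count stops at Day 168 and last contact for a rollover patient is taken as Day 196. For an event that few patients have, the denominator grows by up to 196/168, so the rate falls to at most 168/196 = 0.857 of its value, 14.3% lower. If last contact is taken as the Week 24 visit, there is no shift. The SAP does not say which applies.

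**The case against.** **Footnote o is not a rival rule.** The footnote never names Week 24. That end comes from joining it to Section 7.2.5, and its last sentence sends the reader to 10.1.1. This stands, and 10.1.1 may be meant to govern. But then open-label days fall inside this study's reporting period, so the cross-reference chooses between the two consequences and does not remove the problem.

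**Open-label events will not count against placebo.** A reader might infer that early diarrhea on open-label odevixibat would be tabulated under placebo and shrink the safety difference. The documents do not support that. The SAP governs the TEAE tables and counts only events in the Treatment Period, which is given as 24 weeks. Protocol Section 10.1.2.1 also describes an AE as something occurring in the study, and Section 7.2.5 ends a rollover patient's participation at Week 24. SAP Table 10.1 already treats rollover patients separately, giving the follow-up window only to those who do not roll over. The objection largely stands. What remains is that the protocol's own TEAE definition has no end, the SAP names no end day, and Table 10.1 concerns by-visit summaries, not AEs.

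**Last contact in this study is naturally Week 24 for these patients.** That is plausible, but Table 9 does not say so, and a contact at Day 196 under 10.1.1 would also qualify.

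**The off-drug gap may be covered elsewhere.** The extension protocol is not among the documents and may collect these events. The claim is therefore limited to what this study collects.

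**The number affected is unknown.** A reader might also infer that most patients are involved, since completers are invited. Section 7.1.2.2.5 makes entry optional and subject to that study's eligibility criteria, and no uptake is stated. The figures above are upper bounds only.

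**Conclusion.** The point holds as an inconsistency in safety data collection, with a related gap in the SAP. For rollover patients the protocol supports two AE/SAE end dates, about Day 168 and about Day 196, and neither is tied to the first open-label dose. In the SAP, the TEAE count and the time at risk are not made to end on the same day.

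The size is at most 28 days per rollover patient. For placebo that is 0.92 patient-years against 5.52, assuming that all 12 expected completers roll over and take drug to Week 24, and it is shared between off-drug and open-label time in a proportion the documents do not give. With same-day rollover, stopping at Week 24 loses no off-drug time.

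The documents do not show that placebo TEAE rates will be contaminated; the SAP's Treatment Period restriction probably prevents it. No efficacy endpoint, sample size or alpha is affected. This is a minor-to-moderate correction, worth making because it bears on SAE capture and on the exposure-adjusted rates.

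**What to change.** **Protocol.** Reconcile Section 10.1.1, Table 1 footnote o and Section 7.2.5. For patients who enter the extension, AE and SAE collection in this study ends at the first open-label dose or 28 days after the last randomised dose, whichever is earlier. This covers any off-drug gap and excludes open-label days. Put the matching end into the TEAE definition in Section 10.1.3.

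**SAP.** State the end day of the TEAE period in Section 4.8.1 and Table 9. For rollover patients, use the date above to end both the TEAE period and time at risk, and to censor the Kaplan-Meier curves. State the end day for the other patients too, since their last contact is normally the Safety Follow-up visit at about Day 196.

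**Cost.** Wording in four protocol places, one SAP derivation, and the date of first open-label dose from the extension database. AE questions can be asked at the contact at which the patient enters the extension, so no visit is added. For patients who have already rolled over, the protocol wording cannot change what was collected, but the SAP rule can still be fixed before database lock.
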